Study design: Randomized, double blinded, sham controlled study.

Sample size: The study of Eun Kyoung Kang, et al observed that post-stimulation response accuracy in tDCS was 31.9 ± 6.9 and in Sham stimulation was 29.9 ± 6.2 . Taking these values as reference, the minimum required sample size with 80% power of study and 5% level of significance is 169 patients in each study group. For finite sample size taking population as 20, total sample size calculated is 19. To reduce margin of error, total sample size taken is 20 (10 per group).

Formula used is:

For comparing mean of two groups

$$N \geq 2(\text{standard deviation})^2 \times (Z\alpha + Z\beta)^2 (\text{mean difference})^2$$

Where $Z\alpha$ is value of Z (normal variate) at two sided alpha error of 5% and $Z\beta$ is value of Z (normal variate) at power of 80% and mean difference is difference in mean values of two groups.

$$\text{Pooled standard deviation} = \sqrt{(S1^2 + S2^2)/2}$$

Where S1 is standard deviation of 1 group. and S2 is standard deviation of other group. Finite population correction factor:-

$$SS \geq n / (1 + [(n - 1)/\text{Pop}])$$

Where Pop is population

Calculations:

$$\text{Pooled standard deviation} =$$

$$= 6.56$$

$$N \geq 2(6.56)^2 \times (1.96 + .84)^2 (2)^2$$

$$\geq 168.66 = 169 (\text{approx.})$$

$$\sqrt{(6.92 + 6.22)/2}$$

So total sample size to be taken is $169 \times 2 = 338$

Finite population correction factor:-

$$SS \geq 338 / (1 + [(338 - 1)/20])$$

$$\geq 18.93 = 19 (\text{approx.})$$

Assuming 20% attrition, each group will consist of at least 12 patients.

Block Randomization

Block Randomization with Sealed Envelope System: - In this technique, patients will be randomized in a series of blocks of 4, using an online randomization generator. Patients will be allocated to either of the groups (group A - true or group B- sham) in a 1:1 ratio. The randomization list will be generated by the biostatistician and transferred to a sealed opaque envelope, and each envelope will be opened by the primary investigator (supervisor) when the corresponding number of eligible participants is enrolled. However, the technician who administers the anodal tDCS procedure will know about the identity of the groups. A blinded investigator will record outcomes. Neither the patient nor the investigator knows which label represents which group, making this a double-blind study.

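### The sample size rests on an assumed population of 20, yet the plan enrols at least 24; as a smaller point, 12 per group less 20% attrition meets the calculated 19 but not the adopted 20

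*Protocol*

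**What the plan says.** All the figures stand in the protocol, Material and Methods, under Sample size.

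- The inputs come from a cited study: "post-stimulation response accuracy in tDCS was 31.9 ± 6.9 and in Sham stimulation was 29.9 ± 6.2".
- From these the protocol concludes that "the minimum required sample size with 80% power of study and 5% level of significance is 169 patients in each study group", or 338 in total.
- It then applies a finite population correction: "For finite sample size taking population as 20, total sample size calculated is 19".
- The adopted size follows: "To reduce margin of error, total sample size taken is 20 (10 per group").
- The last line allows for losses: "Assuming 20% attrition, each group will consist of at least 12 patients".

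Block Randomization, which follows directly, sets blocks of 4 and equal allocation. At least 12 per group therefore means at least 24 patients randomized, although the protocol does not print that total. Nor does it say what the population of 20 refers to or how 12 was obtained. The Study population entry names a clinical category (aphasic patients with left middle cerebral artery infarcts) and sets no numerical limit.

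**The concern.** The population of 20 is the only step that brings the requirement down from 338 to 19. A trial that plans to enrol at least 24 cannot be drawing from a population of 20, so the paragraph contradicts the assumption on which its result depends. At stake is whether the stated 80% power and 5% significance level have anything to do with the planned size. A reader of the final report who takes the 80% at face value would give a null result far more weight than it can carry.

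The second, smaller matter is which number the trial is meant to deliver. The calculated total is 19, the adopted total is 20, and the enrolment floor implies 24. Under the stated 20% loss, 24 enrolled supports the first of these but not the second. It is then unclear against which number completion should be judged.

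**Working it through.** **Inputs (Protocol, Sample size).** Means 31.9 and 29.9, so a difference of 2; SDs 6.9 and 6.2; two-sided 5% level; 80% power; population 20; attrition 20%; at least 12 per group.

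**1. Reproducing the protocol's figures.**
- Pooled SD = √((6.9² + 6.2²)/2) = 6.56.
- n per group = 2 × 6.56² × (1.96 + 0.84)² / 2² = 168.7, so 169; total 338.
- Correction: 338 / (1 + 337/20) = 338 / 17.85 = 18.94, so 19.

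The protocol's 169, 338 and 19 all reproduce.

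**2. The population of 20 against the planned enrolment.**
- With a population of 20 the correction is n / (1 + (n − 1)/20) = 20n/(n + 19). This is below 20 for every n, however large.
- A planned total of 2 × 12 = 24 therefore cannot be consistent with it. The adopted 20 is already the entire assumed population.
- The result follows the population entered, not the power. Starting from 338, a population of 24 gives 22.5, 100 gives 77.3, and 1000 gives 252.8.

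**3. Power without the correction.** Normal approximation: power = Φ(2 / (6.56 × √(2/n)) − 1.96).

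| n per group | Power for a 2-point difference |
|---|---|
| 9.6 | 9.8% |
| 10 | 10.1% |
| 12 | 11.3% |
| 13 | 11.8% |
| 169 | 80.0% |

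The t-based values for 9.6 to 13 per group are lower by at most 0.3 percentage points.

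**4. Attrition.**
- Expected to remain from the stated floor: 12 × 0.8 = 9.6 per group; 24 × 0.8 = 19.2 in total.
- Needed to keep the adopted 10 per group: 10 / 0.8 = 12.5, so 13 per group, 26 in total.
- Needed to keep the calculated 19: 19 / 0.8 = 23.75, so 24, or 12 per group.
- 12 also equals 10 × 1.2. Two routes lead to 12, and the protocol shows neither.

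**5. What the shortfall costs in precision.** 95% CI half-width = t × SD × √(2/n), with 2n − 2 degrees of freedom and SD 6.56 assumed.
- n = 9.6: 2.108 × 6.56 × √(2/9.6) = 6.31.
- n = 10: 2.101 × 6.56 × √(2/10) = 6.16.
- Difference: about 0.15 points.

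**6. Whether that SD applies.** It describes a post-stimulation score in the cited study. The primary objective here is the difference in change in Accuracy. The protocol defines Accuracy as a count of uncued names on a test of 30 drawings, so it cannot exceed 30; the reference mean of 31.9 does. The half-widths are conditional on an SD from another measure.

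**The case against.** The attrition line can be defended. The protocol says at least 12, which is a floor that 13 per group would also satisfy, and 12 per group follows correctly from the calculated 19. Calculated, adopted and attrition-inflated totals are ordinary successive steps, so printing different numbers is not in itself a fault. All of this stands.

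A reader might infer that the protocol made the familiar mistake of multiplying by 1.2 instead of dividing by 0.8. The document does not show that step, and the other route fits equally well. What remains is narrower: having moved from 19 to 20, the protocol states a minimum that does not preserve 20 under its own loss rate.

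A reader might also infer a material loss of precision by looking at 9 per group. That would be 18 of 24 retained, a 25% loss and not the stated 20%. At 9.6 per group the change is about 0.15 points and no conclusion turns on it.

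On the population, it could be argued that 20 was meant as the number of eligible patients the site expects to see. The protocol does not say so. If it did, the plan to enrol at least 24 would contradict it just the same.

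**Conclusion.** The point holds, with its weight on the population. A size obtained by assuming 20 patients exist is incompatible with enrolling at least 24, and nothing else in the paragraph connects 338 to 19. The stated 80% power therefore does not attach to the planned size; on the protocol's own difference and SD it is about 10%. That figure takes the cited study's values at face value, as the protocol does.

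The attrition mismatch is real but minor: 0.4 expected patients per group against the adopted 10, and none against the calculated 19.

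It would be tempting to read this as a case for enrolling 13 per group. The documents do not support that as a remedy, because 26 patients also exceed a population of 20 and power would be about 12%. Nor do the figures show that a trial of this size is not worth doing. They show that its size needs a different justification.

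**What to change.** Rewrite the sample size paragraph as follows.

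- Keep 24 enrolled, 12 per group. This is divisible by the block of 4, whereas 26 is not.
- State an evaluable target that agrees with 20% attrition: about 19 in total, 9 to 10 per group.
- Remove the finite population correction, and with it the statement that this size follows from 80% power. The two must go together, because without the correction the calculation returns 338.
- Justify the size by feasibility and expected precision: a 95% CI half-width of about 6.3 points at 9.6 per group, against 6.2 at 10 per group. Say plainly that this assumes SD 6.56 from the cited study's post-stimulation score, not the SD of change on the 30-item test.

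The cost is a rewritten paragraph, not a one-sentence edit, and a less favourable stated power. No extra patients are needed.

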Study population: Aphasic patients with acute ischemic stroke with left Middle Cerebral Artery territory infarcts.

INCLUSION CRITERIA

- Aphasic patients with left middle cerebral artery territory Acute Ischemic Stroke
- Patients between 18-65 years of age.
- Within 5 days of onset of stroke.

EXCLUSION CRITERIA

- Patients with malignant Middle Cerebral Artery territory infarcts and previous clinical history of cerebral hemisphere stroke.
- Patients with history of previous brain surgery or skull defect due to surgery e.g. craniectomy.
- Patients with epilepsy.
- Patients with history of significant head trauma in the last 1 month.
- Patients with documented history of major depression prior to stroke.
- Patients with alcohol/drug abuse in the past 6 months.
- Patients with prior significant cognitive impairment.
- Pacemaker in-situ, cochlear implant in-situ.
- Pregnancy.

PROCEDURAL DETAILS

- All consenting patients recruited for the study will be evaluated clinically in detail. The patients will undergo aphasia testing using the Western Aphasia Battery and will be classified accordingly into the subtypes of aphasia. The patients will then be randomized into either the true stimulation group or the sham stimulation group as mentioned.

Picture Naming Test

- The Indian Council of Medical Research (ICMR) validated the Picture Naming Test (PNT), part of the ICMR MUDRA Toolbox for use in patients with Dementia. The PNT was used to objectively quantify Naming ability during and after sessions of anodal Transcranial Direct Current Stimulation. The ICMR PNT has been validated in five languages, including English and Hindi.
- The ICMR PNT consists of 30 line drawings.
- The administration of the test is as follows:
 - The pictures are shown one by one.
 - The subject has to identify each item by telling the first name that comes to their mind upon seeing the stimulus. 10 seconds are given for an unprompted response.

- If the subject is unable to name the image shown or makes an error during naming, cues are provided.
 - First, a category/semantic cue is provided, and the patient is given 10 seconds to name the picture.
 - If the subject fails to respond or responds incorrectly, a phonemic cue is provided, and the subject is again given 10 seconds to respond.
 - If the subject is still unable to respond or makes an error, the test moves on to the next picture.
 - Hence, the maximum time for naming an image is 30 seconds.

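### The printed A/B key and envelope opening by the primary investigator contradict the stated label masking, and fixed blocks of 4 let anyone who sees past allocations know about a third of later ones

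*Protocol*

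**What the plan says.** The procedure is in the Block Randomization paragraph of the protocol (Material and Methods).

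- **List:** "patients will be randomized in a series of blocks of 4, using an online randomization generator". No other block size and no stratification are mentioned, and Place of Study names one department.
- **Labels:** "Patients will be allocated to either of the groups (group A - true or group B- sham) in a 1:1 ratio".
- **Concealment:** the biostatistician prepares the list, and the envelopes are sealed and opaque. On their opening, the text reads: "each envelope will be opened by the primary investigator (supervisor) when the corresponding number of eligible participants is enrolled".
- **Who is unblinded:** "the technician who administers the anodal tDCS procedure will know about the identity of the groups".
- **Who assesses:** "A blinded investigator will record outcomes".
- **Conclusion drawn:** "Neither the patient nor the investigator knows which label represents which group, making this a double-blind study".

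Procedural Details puts consent and the Western Aphasia Battery first and continues: "The patients will then be randomized into either the true stimulation group or the sham stimulation group as mentioned". The baseline Picture Naming Test (PNT) falls on Day 0, before the first session. The protocol does not say whether it comes before or after the envelope is opened.

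**The concern.** The reason given for the double blind is that the investigator cannot decode the labels. The same paragraph decodes them and hands each patient's label to the primary investigator. Whatever blinding the trial achieves, it is not achieved in the way the protocol describes.

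Two things are at stake.

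- **Concealment of later allocations.** The person who opens every envelope has the full allocation history, and the block size is printed. If that person also has a say in who is enrolled, some upcoming allocations are known before the decision is made.
- **Blinding of measurements.** Accuracy and reaction time on the PNT depend on how cues are given, which responses are accepted and when a hand-held stopwatch is paused. Both co-primary endpoints are changes from baseline, so the Day 0 measurement needs the same protection as Day 5. The protocol does not say that the blinded assessor is someone other than the envelope opener, or that the Day 0 PNT is finished before the allocation is revealed.

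**Working it through.** **1. The statements side by side**

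| Statement in the Block Randomization paragraph | Consequence |
|---|---|
| The key is printed: A is true, B is sham | Any reader of the protocol can decode a label |
| The primary investigator opens each envelope | That person learns every patient's label |
| The investigator does not know what the labels mean | Untrue of the primary investigator, and untrue of any other investigator who has read the protocol |

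The first two rows together unblind the primary investigator. The first row alone defeats the claim that the labels cannot be decoded. An investigator who has read the protocol stays blind only by never seeing a patient's label, and the paragraph does not state that safeguard.

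**2. Predictability in blocks of 4**

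The protocol gives no figure for predictability, so there is none to reproduce. Inputs from the protocol are block size 4, ratio 1:1 and a total of 20 patients, or 24 with at least 12 per group after the attrition allowance. Assumptions are that the person knows the block size and has seen all earlier allocations in a single sequence.

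The six equally likely blocks are AABB, ABAB, ABBA, BAAB, BABA and BBAA.

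*Allocations known for certain beforehand*

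- Positions 1 and 2: never.
- Position 3: only when positions 1 and 2 match (AABB, BBAA), so 2/6 = 0.333.
- Position 4: always, so 1.
- Total per block: 0.333 + 1 = 1.333. Share: 1.333/4 = 33.3%.
- Of 20 patients: 20 × 0.333 = 6.7. Of 24: 24 × 0.333 = 8.

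*Correct guesses when always naming the arm with more places left*

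- Position 1: 1/2 = 0.500.
- Position 2: two of the three remaining places belong to the other arm, so 2/3 = 0.667.
- Position 3: certain with probability 1/3, otherwise an even guess, so 1/3 × 1 + 2/3 × 1/2 = 0.667.
- Position 4: 1.
- Total per block: 0.500 + 0.667 + 0.667 + 1 = 2.833. Share: 2.833/4 = 70.8%, against 50% under full concealment.
- Of 20 patients: 14.2. Of 24: 17.

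**3. How much of this is due to the number 4**

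| Fixed block size | Known for certain | Guessed correctly |
|---|---|---|
| 4 | 33.3% | 70.8% |
| 6 | 25.0% | 68.3% |
| 8 | 20.0% | 66.6% |

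A larger fixed block reduces certainty but barely reduces successful guessing. What matters most is who sees the history and whether that person has a part in enrolment.

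**The case against.** A reader might infer that concealment and the double blind both fail outright. The documents do not support that.

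- **Concealment has real safeguards.** The biostatistician makes the list, the envelopes are sealed and opaque, and each is opened only when its participant is enrolled. Opening at that point does not break concealment for that patient. Prediction of later allocations matters only if the opener influences enrolment, and the protocol does not say who enrols. The 33% and 70.8% are therefore conditional figures.
- **Patient blinding is not shown to fail.** Under tDCS Parameters, the control group receives a sham procedure.
- **Assessor blinding is not shown to fail.** The protocol assigns outcome recording to a blinded investigator. The sentence about label ignorance follows directly and may refer to that person rather than to the primary investigator (supervisor). On this reading, opening the envelopes does not contradict it. The printed key still does, because the assessor's blind would then rest on not seeing labels rather than on being unable to decode them.
- **Scoring discretion is limited** by prespecified accepted names and fixed 10-second windows, and nothing places the supervisor in PNT delivery.
- **Blocks of 4 are a common choice** for a trial of this size, and with separate roles their predictability would do little harm.

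A reader might also infer that selective enrolment by aphasia severity would outweigh any treatment effect. The documents give no figure for how severity affects change in naming, so that conclusion cannot be drawn.

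These points limit the consequences. They do not remove the contradiction, and they do not supply the missing statement that enroller, envelope opener and assessor are different people.

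**Conclusion.** The blinding statement is contradicted within its own paragraph. The primary investigator cannot be counted as blind, and label masking does not work as described. This part rests on the text alone and is firm.

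The threat to concealment is conditional. In one sequence with a disclosed fixed block of 4, a person who has seen earlier allocations knows 33% of allocations for certain (about 7 of 20 or 8 of 24) and guesses 70.8% correctly. It becomes a source of bias only if that person also influences enrolment, which the protocol neither states nor excludes. Patient and assessor blinding may hold, the latter if the assessor is a different person shielded from labels and envelopes. Severity: should be fixed.

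**What to change.** Amend the Block Randomization paragraph as follows.

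1. The technician, who is unblinded already, opens each envelope, and only after enrolment and the Day 0 PNT are complete. The technician takes no part in enrolment or PNT scoring. This condition is essential, because the technician would otherwise have the same foreknowledge.
2. Replace the printed A/B key with neutral codes whose meaning is held by the biostatistician and the technician.
3. Use randomly varying block sizes and keep them out of text that site staff read.
4. State that the outcome assessor is not the person who opens the envelopes and sees neither labels nor envelopes. State also who enrols.
5. Limit the blinding statement to the patient and the outcome assessor.

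The cost is a short protocol change and a regenerated list, with no extra staff. Varying block sizes may leave the arms unequal by one or two patients.
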